3.2.1 Primary outcomes

Primary outcomes will be the change in bacterial load compared to baseline. (see appendix A – molecular microbiology protocol for details on quantification). [name] laboratory at UM Miller School of Medicine, Department of Dermatology and Cutaneous Surgery will be the coordinating center responsible for tissue sample receipt and

processing. Bacterial load in CFU/g among treatment and control arms will be calculated for each wound at visits T0, T2 and T3. The trajectories of bacterial load for each subjects and average change in bacterial load between groups will be compared.

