6.3 Handling missed visits

It is preferred that subjects are seen at regular intervals. However, this may not be possible at times. If a subject needs to miss a visit, every effort should be made to reschedule as close as possible to the original date and then resume following visits at the original intervals. For example, if a subject regularly visits on Wednesdays and will miss a visit and a makeup visit is scheduled for that Friday, the next visit should return to the original intervals and be scheduled for the next Wednesday.

6.4 Stopping rule:

The PI may decide to stop the trial due to safety concerns at any time during the trial. The PI may consult the local Institutional Review Board (IRB) and/or Sponsor for safety related decisions.

7 Statistical methods

This study is a single center randomized longitudinal pilot study to investigate the effectiveness of Cutimed® Sorbact® (Study Device) compared to Comparator (silver impregnated contact layer dressing - Acticoat®) in modifying bacterial load in venous leg ulcers (VLU). Efficacy will be measured as the difference in change in bacterial load compared to baseline between two study arms i.e. Study Device vs. Comparator. This study will also

compare bacterial silver resistance based on genetic and phenotypic characterization over time, healing rate, complete healing at 6 weeks, pain, quality of life (QOL) measurements and adverse events as secondary endpoints.

We expect to study n=30 subjects for both the primary and secondary endpoints. The number of subjects estimated for the study (n=30) is not based on hypothesis driven statistical power calculation. Rather, as a pilot study, a goal for this investigation is to generate effect estimates that will assist in determining an appropriate sample size for future studies.

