Prior to performing statistical analyses on quantitative study data, the data will be checked, screened and verified to ensure the integrity of the database. Data screening will focus on several aspects. We will determine the amount, the pattern, and randomness of missing data. We will define outliers as observations that appear to be very high or very low, and decide how to proceed based on the presumed cause. We will identify inconsistencies within a single variable and between variables. Initially, we will perform an explanatory data analysis; visually via graphics/plots and numerically by descriptive statistics with mean, standard deviation for measurements taken on a continuous scale, and frequencies and percentages, various types of cross-tabulations for measurements taken on a categorical scale. Corresponding confidence intervals (CI) for means and proportions will be calculated. To have a better understanding of the relationships among different study measurements, parametric or non-parametric correlation coefficients, bivariate/multidimensional cross-tabulations will be constructed. All the descriptive statistics will be reported for all subjects and by study arm.

The primary endpoint of the study, the bacterial load in CFU/g, will be calculated for each wound at visits T0, T2 and T3 among Study Device and Comparator arms. The difference in means of the bacterial load from T3 to T0 will be calculated and compared between study arms with Student's t-test. To be able to study the trajectories of the bacterial load over time, overall and by study arms, the time series plots will be depicted and repeated measures regression analysis will be performed where time and study arm as the main effects. Types of variance-covariance matrix will be determined by standard statistical procedures. We plan to expand the regression model and include other subject characteristics for additional covariate adjustment. Adjusted regression coefficients and corresponding 95% confidence interval (95%CI) will be reported for the study arm as the main effect in the regression models.

The secondary endpoints such as microbiological outcomes, clinical wound outcomes, pain related outcomes, quality of life measurements, and safety outcomes will be analyzed with similar statistical methods as the primary endpoint.

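### The repeated-measures model has only time and arm main effects, so with T0 as a response its reported arm coefficient is not the difference in change from baseline

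*Combined protocol and SAP*

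**What the plan says.** Section 7 (Statistical methods) sets the target: "Efficacy will be measured as the difference in change in bacterial load compared to baseline between two study arms". Section 3.2.1 adds: "The trajectories of bacterial load for each subjects and average change in bacterial load between groups will be compared". Load is calculated for each wound at T0, T2 and T3. Appendix A defines T0 as pre-randomisation.

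Section 7 plans two inferential analyses of the primary endpoint:

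- A Student's t-test: "The difference in means of the bacterial load from T3 to T0 will be calculated and compared between study arms".
- A model for the trajectories, overall and by arm: "repeated measures regression analysis will be performed where time and study arm as the main effects". Its covariance is left open: "Types of variance-covariance matrix will be determined by standard statistical procedures". Other subject characteristics may be added as covariates. Adjusted coefficients with 95% CIs "will be reported for the study arm as the main effect in the regression models".

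The next paragraph says that the secondary endpoints "will be analyzed with similar statistical methods as the primary endpoint". On purpose, section 7 says that "a goal for this investigation is to generate effect estimates that will assist in determining an appropriate sample size for future studies". An arm-by-time term is not named anywhere. Neither is baseline load as a covariate, nor a baseline mean common to both arms.

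**The concern.** A difference in change is a follow-up arm difference minus the T0 arm difference. In a longitudinal model with T0 among the responses, that quantity is the arm-by-time term. The arm main effect is a different quantity: a weighted average of the arm differences at all visits, T0 included. Randomisation makes the expected T0 difference zero, so including T0 normally pulls the coefficient towards zero. Any chance T0 difference is added in, where a change score would subtract it. Without an interaction the two arms are also forced onto parallel profiles, so the model cannot compare trajectories by arm, which is why it was introduced.

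The report would then hold two estimates of different quantities: an unadjusted T3 minus T0 difference, and a covariate-adjusted arm coefficient with a CI. A reader could easily take the second for the adjusted version of the first and carry it into the design of the next trial. Secondary endpoints measured repeatedly from T0 and modelled in the same way, such as quality of life and silver resistance over time, would inherit the problem.

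**Working it through.** The plan states no figure to reproduce: n=30 is explicitly not power-based, and no SD, correlation or effect size is given. The check therefore asks what the coefficient estimates.

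**Inputs from the documents:** visits T0, T2 and T3; T0 before randomisation; 15 per arm (section 4.1, Appendix A); alpha 5% (taken as two-sided).
**Assumed:** visit SD 1, correlation r between visits, and the effect sizes shown.

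**1. What the arm coefficient is.** Let d = (d_T0, d_T2, d_T3) be the arm differences in means and V the within-subject covariance. With complete data, the generalised least squares arm coefficient in a time + arm model is w'd, with w = V⁻¹1 / (1'V⁻¹1). The plan's target at T3 is d_T3 − d_T0. With equal variances and equal correlations, every weight is 1/3 whatever r is.

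**2. Size, with d_T0 = 0 and a T3 effect of 1:**

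| T2 effect | Arm coefficient | Share of T3 effect |
|---|---|---|
| 1 | (0+1+1)/3 | 67% |
| 0.5 | (0+0.5+1)/3 | 50% |
| 0 | (0+0+1)/3 | 33% |
| 1.5 | (0+1.5+1)/3 | 83% |
| 2 | (0+2+1)/3 | 100% |

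In 20,000 simulated trials (15 per arm, r = 0.5, true effect −1 at T2 and T3), the arm coefficient averaged −0.665 and the difference in change −1.003.

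**3. Chance imbalance.** With d = (0.5, 0.5, 0.5) there is no difference in change, so the target is 0. The weights sum to 1, so the coefficient is 0.5 under any covariance. At r = 0.5 with no treatment effect, the coefficient correlates with the T0 difference at √((1+2r)/3) = 0.82.

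**4. Dependence on the covariance chosen** (r = 0.5, equal T2 and T3 effects). If the T0 SD is two thirds of the later SD, the weight on T0 is 0.79 and the coefficient is 21% of the effect. If the T0 SD is 1.5 times the later SD, the weight on T0 is 0 and the coefficient is 100%. The quantity estimated therefore depends on a covariance that will be picked from the data.

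**5. Missing T3.** If 20% in each arm lack T3 completely at random (r = 0.5), the 67/50/33% become 64/45/27%. Appendix A ties the T3 result to an area reduction below 75%; that outcome-dependent rule is not modelled here.

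**6. Coverage and power** (15 per arm, 28 df, noncentral t, r = 0.5). The subject mean has variance (1+2r)/3 = 0.667; the change score has variance 2(1−r) = 1.

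| T2 effect as share of T3 | 95% CI covers T3 effect, 1 SD | Same, 0.5 SD | Power at 1 SD |
|---|---|---|---|
| all | 81% | 92% | 58% |
| half | 63% | 87% | 37% |
| none | 42% | 81% | 19% |

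The plan's own T3 minus T0 t-test has 75% power at 1 SD. At r = 0.3 with a constant effect the order reverses: 68% for the arm coefficient against 61% for the t-test. With no effect, the test of the arm coefficient rejects 5% of the time.

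**7. Use for planning.** If the coefficient replaced the T3 effect and the SD were left unchanged, the next sample size would be multiplied by 1/0.667² = 2.25, 1/0.5² = 4 or 1/0.333² = 9. If instead the coefficient is paired with its own subject-mean SD and compared with a change-score design, the ratio for a constant effect is [(1+2r)/3 ÷ (2/3)²] / [2(1−r)], which is 0.86 at r = 0.3, 1.5 at r = 0.5 and 3.0 at r = 0.7.

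**8. Effect of the repair.** In one large simulated data set (2,000 per arm, true effect −1 at T2 and T3), the main-effects model gave −0.67. Adding arm-by-time gave −0.99 for the T3 contrast. T0 as covariate with T2 and T3 as responses gave an arm effect of −0.98, which is the average over the two visits.

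**The case against.** The strongest reply is that the plan never says T0 is a response row. Calculating load at three visits describes measurement, and the outcome is defined as change. If changes at T2 and T3 were the responses, or T0 a covariate, the arm coefficient would be a legitimate average effect. This stands as a condition on the dilution. It does not rescue the text: T0 is listed alongside T2 and T3 as a value of the endpoint, the model is meant to show load over time, and the covariates mentioned are other subject characteristics. Even on the kinder reading, the arms are still forced to be parallel.

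The t-test matches the efficacy definition and is unaffected; that stands in full. Section 7 also allows other models, but these are unspecified and prompted by possible convergence failure.

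Not all of the shortfall is due to T0. With T2 and T3 alone, the coefficient would be 100%, 75% or 50% of the T3 effect in the first three scenarios; T0 contributes the further factor of 2/3. The 2.25/4/9 multiples need an unchanged SD, and at r = 0.3 the own-SD ratio reverses direction. Both points stand.

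Carry-over to the secondary endpoints is limited: healing rate is already a change, complete healing is a proportion at F1, and the pain outcomes in section 3.2.2 are times to an event.

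**Conclusion.** The concern holds and should be fixed. On the natural reading of section 7, the adjusted arm coefficient does not estimate the plan's own efficacy measure, and no reading of a main-effects model lets trajectories differ by arm. In the base illustration the coefficient is 67% of the T3 effect if the effect is constant, and less if it is still building; the cases examined run from 21% to 100%. All of these sizes rest on assumed variances, correlations and effects. That the arm coefficient is not a difference in change follows from the model alone, given T0 as a response. This is an error in what is estimated, not in type 1 error, and it leaves the T3 minus T0 t-test intact. It matters here because effect estimates are a stated product of the pilot.

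**What to change.** In section 7, replace the main-effects sentence with a model that has T2 and T3 as responses, T0 load as a baseline covariate (or all three visits with one T0 mean common to both arms), and time, arm and arm-by-time terms. State that the adjusted treatment effect is the arm contrast at T3, with the T2 contrast alongside, each with a 95% CI. Keep the T3 minus T0 t-test and say that both analyses target the T3 difference. Use the same form for the secondary endpoints that are modelled repeatedly from T0.

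The cost is one sentence, no new data, and about one extra parameter, which is small at n=30.

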3.2.2 Secondary outcomes

Secondary outcomes will include:

Microbiological outcomes: bacterial silver resistance characterization on molecular and phenotypic level over time (see appendix A for molecular microbiology protocol).

Clinical wound outcomes: healing rate and percent reduction in area over 6 weeks will be calculated by measuring wound area at each visit and dividing the area change by 6 to calculate average wound healing rate in cm^2/week and the average percent reduction for each study arm.

Complete healing at 6 weeks – the proportion of subjects in each study arm in which the study ulcer achieved complete healing at visit F1.

Pain related outcomes: pain assessments will be collected at every visit using visual analog scale (VAS) and time from visit T0 to clinically meaningful decrease in pain (i.e. 33% reduction from baseline) [21] will be calculated. Additionally, time to first indication of no pain will be calculated (i.e. VAS < 5mm)

Quality of life measurements: the EQ-5D-5L [22] and the Wound Quality of Life (WQoL) [23, 24] instruments will be used and assessments take place at visits T0, T4 and F1.

Safety outcomes: adverse events will be recorded at every visit and type and frequency logged and compared between arms.

4. Study population

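### The two times to pain relief are assigned methods modelled on a t-test and repeated measures regression, with no survival method and no rule for subjects who never reach the event

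*Combined protocol and SAP*

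**What the plan says.** Section 7 specifies the primary analysis in two parts. The change in bacterial load from T0 to T3 is "compared between study arms with Student's t-test". For the trajectory over T0, T2 and T3, "repeated measures regression analysis will be performed where time and study arm as the main effects". No distribution, link function or treatment of censoring is stated.

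One sentence then covers the microbiological, wound, pain, quality of life and safety outcomes together: they "will be analyzed with similar statistical methods as the primary endpoint".

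Section 3.2.2 shows that these outcomes are of different kinds. One pain outcome is the "time from visit T0 to clinically meaningful decrease in pain", defined as a 33% reduction. The other is the time to a first VAS below 5 mm. Complete healing is "the proportion of subjects in each study arm in which the study ulcer achieved complete healing at visit F1". Adverse events are compared between arms by type and frequency. Appendix A adds PCR detection of silE, silP and silS, a yes/no result at each tissue sample.

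Section 7 also plans frequencies, percentages and cross-tabulations for categorical data, confidence intervals for proportions (type not given), transformations where indicated, and possibly other regression models if the planned ones do not converge.

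**The concern.** A subject whose pain has not fallen by 33%, or has not gone below 5 mm, by the last visit has no event time. All that is known is that the time is longer than the time observed. A t-test or an ordinary regression needs a number for every subject. The analyst must therefore leave such subjects out or give them an invented time, and the plan says neither which nor how.

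The choice matters most where the arms differ. The worse arm has more subjects without the event, so leaving them out removes its poorest results and pulls the two means together. Section 7 gives the purpose of the pilot as producing effect estimates to size later studies. An estimate shrunk in this way would mislead that planning.

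A lesser issue affects rare yes/no outcomes, such as single types of adverse event or a seldom-detected gene. There, intervals based on the t distribution break down.

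**Working it through.** **Plan's own figure.** There is none to reproduce on this point. Section 7 says that the sample size does not come from a power calculation, and no event rate for pain is given.

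**Inputs.** 15 completers per arm (section 4.1 and Appendix A; the Executive Summary's 45 subjects is a separate inconsistency). Visits T1 to T4 at weeks 1, 2, 3 and 4, and F1 two weeks after T4, hence week 6 (section 3.1 and Table 1). Alpha 5% (section 7), taken as two-sided. *Assumed:* event rates, shown as a range; constant hazard; complete follow-up.

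**Model.** For a proportion P with the event by week 6, the weekly hazard is h = -ln(1 - P)/6. The event is recorded at the first visit at or after it occurs, so the probability of recording it at visit v(k) is exp(-h v(k-1)) - exp(-h v(k)).

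**One case in full: 30% vs 60%.**
- Hazards: -ln(0.70)/6 = 0.0594 and -ln(0.40)/6 = 0.1527, ratio 2.57.
- Expected subjects without the event: 15 x 0.70 = 10.5 and 15 x 0.40 = 6.0. Only 30 - 16.5 = 13.5 of 30 have a time.
- Mean recorded time among those with the event: 3.48 vs 3.19 weeks, a difference of 0.29 week.
- Mean with the others set to week 6: 5.24 vs 4.31 weeks, a difference of 0.93 week. This is the true difference in mean time restricted to six weeks on this visit grid.

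**Simulation** (20,000 trials per row; 10,000 for the row with medians). Differences are in weeks; percentages are the share of trials with p < 0.05.

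| Assumed 6-week event rates | Hazard ratio | Expected without event, per arm | t-test, such subjects dropped | t-test, set to week 6 | Log-rank |
|---|---|---|---|---|---|
| 30% vs 60% | 2.57 | 10.5 and 6.0 | 0.29; 5.9% | 0.93; 28.8% | 39.5% |
| 30% vs 80% | 4.51 | 10.5 and 3.0 | 0.62; 10.1% | 1.76; 71.4% | 84.4% |
| 50% vs 87.5% (medians 6 vs 2 weeks) | 3.00 | 7.5 and 1.9 | 0.66; 14% | 1.59; 58% | 69% |
| 50% vs 90% | 3.32 | 7.5 and 1.5 | 0.75; 16.1% | 1.75; 67.0% | 77.1% |

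With equal arms (30% or 50% in both), all three approaches reject in 4.9% to 5.3% of trials. The harm is therefore a shrunken estimate and lost power, not false positives.

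**Rare yes/no outcomes, 15 per arm.** The t-based interval for one arm is p ± 2.145 x sqrt(p(1 - p)/14), where p is the observed proportion. With no events it collapses to the single point zero.
- True rate 5%: no events with probability 0.95^15 = 46.3%; coverage 53.6%.
- True rate 10%: 0.90^15 = 20.6%; coverage 79.2%.
- True rates of 20% to 50%: coverage 94.9% to 96.5%, so no problem there.
- No events in either arm: 0.95^30 = 21.5% at a 5% rate and 0.90^30 = 4.2% at 10%. The standard error is then zero and no t statistic exists.

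**The case against.** The plan says similar methods, not identical ones, and does not describe the regression as linear. A logistic or other generalised form is not excluded. Nowhere does the plan say that subjects without the event will be dropped. Setting them to week 6 reproduces the restricted mean difference in the simulation exactly and costs only some power. These are secondary outcomes of an unpowered pilot.

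Much of this stands. Mishandling is a risk that the wording leaves open, not a stated plan. But no reading of similar to a t-test and repeated measures regression supplies a censoring rule. The offer of other regression models is tied to convergence, and a transformation cannot create a time that was not observed. Setting subjects to week 6 is unbiased only if everyone is followed to week 6, whereas section 4.1 allows for up to 15% drop-out. That these outcomes belong to a pilot argues for care with the estimates, not against it.

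Four stronger readings are tempting and are not supported:
- **That a t-test on 0/1 data generally gives p-values that are too favourable.** At 15 per arm its true size is at most 5.5% over rates of 1% to 50%. Fisher's test is conservative, with size at most about 1.7% at the rates tried, which largely explains gaps such as 0.07 vs 0.22 for 0/15 vs 3/15.
- **That a linear model is prescribed.** The text does not say so.
- **That nothing else is planned.** Section 7 does plan cross-tabulations and intervals for proportions.
- **That the estimates should be judged against the full difference in mean times.** With medians of 6 and 2 weeks that is (6 - 2)/ln 2 = 5.8 weeks, but it extrapolates beyond F1 and none of these methods estimates it. The fair target is the 1.59 weeks in the table.

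**Conclusion.** The concern holds for the two pain times. The plan assigns them methods with no valid value for a subject who never reaches the event, and a standard alternative is available at almost no cost. Across the four assumed scenarios, detection is 6% to 16% if such subjects are dropped, 29% to 71% if they are set to week 6, and 39% to 84% with the log-rank test. Dropping them also cuts the estimated difference to less than half of the restricted mean difference (for example 0.29 against 0.93 week).

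The absolute figures rest on assumed event rates, constant hazards, 15 per arm and complete follow-up. The ordering of the three approaches is the same in every scenario tried.

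For yes/no outcomes the finding is narrower: no method of comparison is named, and t-based intervals fail only when events are rare or absent. This should be corrected before unblinding, but it does not threaten the primary analysis.

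**What to change.** Replace the single sentence on secondary endpoints in section 7 with a short list of methods by endpoint:

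- **Times to pain relief:** Kaplan-Meier estimates by arm and a log-rank comparison, or a discrete-time or interval-censored model, since pain is seen only at visits. Censor subjects without the event at their last assessed visit. Exclude subjects with VAS below 5 mm at T0 from the no-pain outcome.
- **Complete healing at F1:** risk difference with a Newcombe or exact interval.
- **Adverse events:** the same, by type, keeping the type and frequency comparison of section 3.2.2. A single any-event comparison would lose it.
- **Silver-resistance genes:** a binary GEE or mixed model over T0, T2 and T3, which keeps the comparison over time. Separate tests for each gene and visit would not.

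The cost is SAP wording and standard procedures in SAS or R, which section 7 already names. No visit, measurement or subject is added.

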Due to the nature of a pilot study with limited sample size, regression models might have convergence problem i.e. regression estimates and corresponding 95%CI might not be estimable.

Therefore, we might explore different regression models as a secondary source of modeling approach. Regression model assumptions will be checked and model diagnostics will be done based on the appropriate statistical tools. Transformations of the data in order to meet statistical assumptions will be undertaken when indicated. Type-1 error will be set to 5% (alpha=0.05) and will be adjusted for multiple comparisons. Standard model diagnostic tools will be used. All of the statistical analyses will be carried out using SAS (SAS Institute Inc., Cary, NC) or R (R Foundation for Statistical Computing, Vienna, Austria. <http://www.R-project.org/>).

8 Regulatory and ethical issues

8.1 protocol institutional approval

The PI will submit the protocol and all related materials (e.g. ICF) for approval by the local Institutional Review Board (IRB) before any study related activity commences. All local and Federal regulatory rules will be followed and a dedicated regulatory monitor will be assigned to the protocol.

8.2 informed consent

During visit S1 and before any study activities are initiated, each subject will be provided with detailed information about the study and ample time to review ICF in order to obtain an informed consent. The subject (or legally authorized representative) will then be given the opportunity to ask any questions about the study and all questions will be answered. The subject (or legally authorized representative) will then sign and date the ICF according to the regulatory and legal requirements. ICF will be signed, dated and retained by the PI as part of the study records. No study related activities or procedures will take place before valid consent is obtained in an ethical manner and without.

In the case of a protocol amendment, the ICF will be revised to reflect said changes as required by IRB. Once revised, the ICF will be signed by all new subjects enrolled from that date forward as well as for all subjects still in the study (i.e. in the screening, treatment or follow up phase) when they are next scheduled to appear for a study visit.

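### Section 7 puts adverse events under the multiplicity-adjusted 5% level and names no between-arm risk difference for them, so an excess of harm becomes harder to flag

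*Combined protocol and SAP*

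**What the plan says.** Section 3.2.2 (Secondary outcomes) promises a between-arm safety comparison: "adverse events will be recorded at every visit and type and frequency logged and compared between arms". It does not say whether subjects or events are counted.

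Section 7 (Statistical methods) counts adverse events among the secondary endpoints ("pain, quality of life (QOL) measurements and adverse events as secondary endpoints") and gives them no method of their own: "and safety outcomes will be analyzed with similar statistical methods as the primary endpoint". The primary methods are Student's t-test on the change from T0 to T3 and a repeated measures regression with time and arm. The section's only statement on error rate is: "Type-1 error will be set to 5% (alpha=0.05) and will be adjusted for multiple comparisons". It gives no adjustment method, no family and no number of comparisons, and does not exempt safety.

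Section 7 also plans intervals. For the descriptive summaries, which are to be reported overall and by arm: "Corresponding confidence intervals (CI) for means and proportions will be calculated". For the models: "Adjusted regression coefficients and corresponding 95% confidence interval (95%CI) will be reported for the study arm as the main effect in the regression models". It then cautions that, with a sample this small, "regression estimates and corresponding 95%CI might not be estimable".

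Sections 4.1 and 7 and Appendix A plan 30 subjects; Section 4.1 aims for 15 completers per arm. Section 7 says that this number does not come from a power calculation and that the aim is to estimate effects.

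**The concern.** Adjusting for multiplicity guards against false claims of benefit. For harms the costlier error is usually the missed signal, and adjustment makes that error more likely. Under a section-wide rule, each added comparison of pain, quality of life or silver resistance raises the excess of harm needed to reach significance. Because the family is undefined, the size of that penalty is open.

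The borrowed methods also fit poorly. A t-test on a change from baseline and a model built for bacterial load do not suit sparse counts of events by type. An event type seen in one arm only is a typical case in which a regression coefficient and its interval cannot be estimated.

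At stake is how the safety comparison in the final report can be read. A non-significant result from this trial would carry little information, and the plan has no sentence to stop a reader from taking it as similar safety of the two dressings.

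**Working it through.** **Inputs from the plan.** Type 1 error 5%, adjusted (Section 7). 1:1 allocation (Section 3.1). 15 completers per arm (Section 4.1).

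**Assumptions, because the plan gives no figure.** Two-sided Fisher's exact test on subjects with an event; Bonferroni adjustment; the event rates; the number of comparisons. Six is used because Section 7 lists six secondary items: silver resistance, healing rate, complete healing, pain, quality of life, adverse events. Ten is shown as a wider case.

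**The plan's own figure.** There is no power or detectable difference for adverse events to reproduce. The enrolment figure of 35 follows from 30 × 1.15 = 34.5, rounded up. Dividing instead, 30/0.85 = 35.3, would give 36. This does not affect the point.

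**Levels.** 0.05; 0.05/6 = 0.00833; 0.05/10 = 0.005.

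**Step 1: counts needed to flag harm.** With equal arms and no events in one of them, the two-sided Fisher p-value for k events in the other is 2 × C(15,k)/C(30,k):

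- k = 5: 2 × 3003/142506 = 0.0421
- k = 6: 2 × 5005/593775 = 0.0169
- k = 7: 2 × 6435/2035800 = 0.0063

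So 5/15 is enough at 5%, but 7/15 is needed at 5%/6. Against 1/15, the p-values for 7, 8 and 9 events are 0.0352, 0.0142 and 0.0052, so the requirement moves from 7/15 to 9/15. Results of 0 versus 5 or 6, and 1 versus 7 or 8, are therefore flagged without adjustment and lost with it.

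**Step 2: chance of missing a true tripling.** Miss rate = 1 − Σ Bin(a; 15, p₁) × Bin(b; 15, p₂), summed over all pairs (a, b) with Fisher p ≤ level.

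| True rates | 5% | 5%/6 | 5%/10 |
|---|---|---|---|
| 5% vs 15% | 97.0% | 99.8% | >99.9% |
| 10% vs 30% | 85.1% | 96.7% | 98.8% |
| 15% vs 45% | 72.5% | 88.7% | 94.3% |
| 20% vs 60% | 55.3% | 76.4% | 84.1% |
| 30% vs 90% | 10.6% | 26.2% | 37.5% |

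**Step 3: share due to adjustment.** For 10% versus 30%, adjusting over six comparisons adds 96.7 − 85.1 = 11.6 points to a miss rate already at 85%. For 20% versus 60% it adds 76.4 − 55.3 = 21.1 points. Sample size accounts for most of the problem.

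**Step 4: sensitivity.** The less conservative uncorrected chi-square test misses 10% versus 30% in 72.2% of trials at 5% and 96.7% at 5%/10. The executive summary gives 45 subjects instead of 30, and these sections need reconciling. With 22 versus 23, Fisher misses 10% versus 30% in 68.8% at 5% and 92.6% at 5%/10, and 20% versus 60% in 24.9% and 58.9%.

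**Step 5: what a risk difference would show.** For 1/15 versus 3/15, Fisher gives p = 0.60. The difference is 13.3 points, with a Newcombe (score-based) 95% interval from −13.2 to +39.1. The p-value alone suggests nothing to see; the interval shows that a large excess has not been excluded. For 0/15 versus 6/15, which would be lost at 5%/6, the difference is 40 points with an interval from +11.3 to +64.3.

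**The case against.** The strongest reply is that this is a pilot that says so. Section 7 discloses that the sample is not power-based and aims at estimation. Even without adjustment, 10% versus 30% is missed 85% of the time, and exempting safety would not cure that. This stands: adjustment aggravates the weakness but is not its main source.

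The adjustment sentence is also too vague to establish that adverse events are meant to be in the family. That stands too. But safety is named as a secondary endpoint under the same methods and nothing takes it out, so the natural reading includes it.

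Three stronger readings are tempting and should not be drawn:

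- *That the plan offers nothing but a significance test.* It plans intervals for proportions, descriptive results by arm, and a 95% interval for the arm coefficient, which the reference to similar methods carries over to safety. What is missing is narrower: a between-arm risk difference for adverse events, from a method that copes with sparse counts.
- *That a tripled event rate would almost always be missed.* At an adjusted level this holds for control rates up to about 10%, not for common events. Section 5.19.2 defines adverse events broadly, so the rate of any adverse event could be well above 10%.
- *That a non-significant comparison will be reported as no difference.* No section says so. There is only no safeguard against that reading.

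Finally, safety action does not wait for this test. Events are solicited at every visit, reported to the IRB and sponsor, and assessed for causality (Sections 5.19.1 to 5.19.4), and Section 6.4 allows the trial to be stopped on safety grounds. These provisions protect individual subjects. They do not repair the between-arm comparison promised in Section 3.2.2.

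**Conclusion.** The point holds as a minor one. As written, Section 7 tests harms at a level reduced for multiplicity, with methods designed for a continuous microbiological outcome, and names no between-arm risk difference for adverse events. At 15 per arm, the assumed adjustment over six comparisons raises the count needed against 0/15 from 5 to 7, and the miss rate from 85% to 97% for 10% versus 30% and from 55% to 76% for 20% versus 60%. These figures rest on Fisher's test, Bonferroni adjustment and event rates that the plan does not state. The direction does not depend on them: any reduction of the level makes a harm signal no easier, and usually harder, to flag. The planned intervals soften the point but do not remove it, because those for proportions are not stated as a contrast between arms and the model-based one may not be estimable.

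**What to change.** In Section 7:

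1. State that the multiplicity adjustment does not apply to safety outcomes.
2. For adverse events, replace the reference to the primary endpoint's methods with per-subject incidence by arm, for each event type and for any SAE, together with the between-arm risk difference and an unadjusted exact or score 95% confidence interval.
3. State that a non-significant difference will not be reported as similar safety.

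The cost is a few sentences and no new data. The downside is that some chance differences in event types will be flagged, which is acceptable in an exploratory pilot. The change does not raise the information in 15 subjects per arm; it makes the remaining uncertainty visible.
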